1.6	6 JUL 2021	Modified to replace the previous Headache Fellow and Sub- Investigator, [name], with the new fellow, [name]. [name] completed his fellowship and is no longer at this site. [name] has been trained on the randomization procedures for this study.
1.7	16 NOV 2021	 Modified to add [name], another new Headache Fellow, to the study team. He has also been trained on the randomization procedures for the study. Also, Section 5.7.2, Handling of Participant Withdrawals or Termination, has been modified to state that we plan to replace participants who withdraw or discontinue the study early. This is being changed to allow for the necessary data collection outlined in Section 9.3, Analysis Datasets, of the Statistical Considerations; data will be analyzed from participants who receive at least one dose of the study drug during the non-blinded phase, and also pass the 2-week washout period in the double-blind phase. In order to capture this data to determine efficacy of the drug, 30 participants must complete all visits through Week 12 of the study (Visit 14). This can only be done if we replace the participants who withdraw or discontinue the study early. The number of participants screened will remain unchanged since Version 1.5 of the protocol, at 50.

[figure not shown]
Statement of Compliance

This study will be conducted in accordance with the Code of Federal Regulations on the Protection of Human Subjects (45 CFR Part 46), 21 CFR Parts 50, 56, 312, and 812 as applicable, any other applicable US government research regulations, and institutional research policies and procedures. The International Conference on Harmonisation ("ICH") Guideline for Good Clinical Practice ("GCP") (sometimes referred to as "ICH-GCP" or "E6") will be applied only to the extent that it is compatible with FDA and DHHS regulations. The Principal Investigator will assure that no deviation from, or changes to the protocol will take place without prior agreement from the sponsor and documented approval from the Institutional Review Board (IRB), except where necessary to eliminate an immediate hazard(s) to the trial participants. All personnel involved in the conduct of this study have completed Human Subjects Protection Training.

Protocol Summary

	· J
Title	A pilot, proof of concept, placebo-controlled, parallel study of the effects of high dose intranasal oxytocin for the treatment of tinnitus
Short Title	High Dose Oxytocin Nasal Spray for Treatment of Tinnitus
Brief Summary	The purpose of this study is to evaluate the effects of high-dose intranasal oxytocin for treating tinnitus. The hypothesis is that high dose intranasal oxytocin can significantly reduce tinnitus severity and disability.
Methodology	Pilot, proof of concept, randomized, placebo-control, parallel study
Endpoint	The primary efficacy endpoint is the area under the VAS curve from baseline for all randomized participants during the blinded study phase. The secondary endpoint, which is exploratory, will be improvement ($p < 0.10$) in the Tinnitus Handicap Inventory Severity Scale (THI)/Clinical Global Impression Scale (CGI) and Tinnitus Functional Index (TFI).
Study Duration	Time from when the study opens to enrollment until completion of data analysis will be approximately 1 year.
Participant Duration	Participant participation will last approximately 4 months and involve about 17 visits.
Duration of IP administration	Investigational product administration will last 15 weeks. The first 9 weeks of this period will involve the administration of active study medication to all participants. During the last 6 weeks, participants will be randomized to receive either placebo or active study medication for the remainder of the study.
Population	We will recruit patients from NYU Langone Medical Center's Departments of Otolaryngology and Neurology. Eligible individuals will be age 18 to 75 with continuous perception of tinnitus for > 6 months, with a normal ENT evaluation within the past year.
Study Sites	NYU Langone Medical Center
Number of participants	50 participants expected to be enrolled with a goal of 30 study participants remaining after accounting for screen failures and participants who withdrew from the study.
Description of Study Agent/Procedure	The investigational product, oxytocin nasal spray (45 units/0.1mL for 100mL) is composed of: oxytocin 10 unit/MG/mannitol trituration (4.500g), magnesium chloride crystals (6.080g), citric acid anhydrous gran. (0.284g), sodium citrate powder (5.660g), sterile water for irrigation (100.000mL), and Pcca Mucolox liquid base (10.000mL). The dose for the oxytocin nasal spray will range from 30 to 45 IU per puff to be administered four times per day, for an equivalent to 120 to 180 IU oxytocin/day.
Reference Therapy	The investigational product will be compared to placebo, a nasal spray consisting of magnesium, chloride crystals, citric acid anhydrous gran., sodium citrate powder, sterile water for irrigation, and Pcca Mucolox liquid base.
Key Procedures	Oxytocin (or placebo) will be self – administered by the study participants daily. Study visits will occur every two weeks, from prior to the baseline week to 15 weeks after baseline, during which patients will be asked to rate the loudness of their tinnitus (VAS scale) and complete the THI questionnaire. Additional questionnaires and urinalysis will be performed at every study visit to monitor sodium levels and osmolality.
Statistical Analysis	The primary analysis is to provide an estimate of the partial eta squared effect size difference between placebo and treatment during the blinded phase of the study as well as to provide initial efficacy, safety and tolerability estimates during the initial open label study phase.

Schematic of Study Design

1 Key Roles

Primary investigator: [name] NYU Langone Medical Center [name] [name] [contact]

Sub-investigator (Headache Fellow): [name], MDNYU Langone Medical Center [name] [name] [contact]

Research Coordinator, Regulatory Specialist, Data Management, and Primary Contact: [name] NYU Langone Medical Center [name] [name] [contact]

2 Introduction, Background Information and Scientific Rationale

2.1 Background Information and Relevant Literature

Tinnitus, the perception of noise in the absence of an external stimulus, is a common, disabling and poorly understood phenomenon. Population based studies estimate the prevalence of tinnitus in the United States to range from 8-23%; in other countries, rates of 5-30% have been reported. In a recent study of adults experiencing tinnitus in the preceding 12 months, it was estimated that 1 in 10 Americans are affected. Fifty-six percent had lived with tinnitus for at least 5 years and 27% had symptoms for more than 15 years. Strikingly, 35% of respondents had nearly continuous tinnitus. More than 7% reported that they considered their tinnitus to be a big or very big problem; which would suggest that 15 million Americans are significantly affected (1). Chronic tinnitus affects approximately 50 million Americans and yet there is currently no FDA-approved first-line treatment for the condition.

Tinnitus is generally divided into two categories: objective and subjective. Objective tinnitus is defined as tinnitus that is audible to another person, often as a result of turbulent blood flow, or muscle or palatal contractions, whereas subjective tinnitus, the most common subtype, is perceived only by the patient and usually occurs in the absence of an acoustic etiology (2).

Originally believed to be an otolaryngologic disorder, recent studies suggest that, in fact, tinnitus is most likely a neurological disorder. Tinnitus is often the result of alterations within parts of the auditory pathways. This pathway encompasses the cochlea in the periphery transiting to the midbrain and terminating in the auditory cortex. Damage to the cochlea produces alterations in neuronal activity in which both cortical and subcortical projections adjust to the lack of output with ensuing changes in neural plasticity. These changes in neuroplasticity result in neuronal hyperactivity at various sites in the auditory pathway (dorsal cochlear nucleus, inferior colliculus, auditory cortex, and the striatum) and ultimately reorganization of the auditory tonotopic map (3).

Outside of the auditory pathways, changes are also noted in the limbic system in patients with chronic tinnitus. These changes are not surprising as there are numerous reports attesting to the emotional and affective comorbidities of tinnitus (4). Imaging studies reveal increased activation in the auditory cortex and amygdala in patients with tinnitus and psychological distress (5).

Oxytocin, a 9-amino-acid neuropeptide, is produced by the magnocellular neurons of the hypothalamus, stored in the posterior pituitary and released into the bloodstream from the posterior lobe of the pituitary gland. Oxytocin plays a role in parturition and lactation, sperm transport and ejaculation, and has been shown to promote social bonding and other pro-social interactions. It is also believed that oxytocin may modulate human fear and anxiety responses (6).

Parenteral administration of oxytocin has long been used for the initiation of labor as well as to control postpartum bleeding. Parenteral oxytocin must be administered in hospital settings with careful monitoring. As oxytocin is structurally and functionally related to vasopressin, it can have a direct antidiuretic properties. Oxytocin has direct renal antidiuretic action by binding to vasopressin and oxytocin receptors in the kidney. When infused at high doses (> 20mU/min), there is a potential for oxytocin cross-reactivity with vasopressin which could result in water retention and a dilutional hyponatremia. This risk is increased when oxytocin is intravenously administered with D5W or when high dose infusion protocols are used (7). Acute pulmonary edema following the use of oxytocin during cesarean section together with other oxytocic drugs has been reported as a rare complication of treatment. (8, 9, 10). Additionally, aqueous oxytocin is heat sensitive and therefore requires refrigeration to maintain potency. To combat this drawback, Milewski et al. studied the stability and absorption of an intranasal dry-powder formulation of oxytocin that did not require refrigeration (11). In this animal study, using cynomolgus monkeys, that have a similar nasal morphology as humans, the authors found that the intranasal route of administration had an approximately 12% relative bioavailability compared with intramuscular dosing.

Based on the partial benefit experienced by the patients, I hypothesized that the dosing paradigm was inadequate and increasing the dose and/or frequency of dosing could increase the duration of symptom improvement. This hypothesis is supported in the literature.

Because the very short plasma half-life of nasally administered oxytocin (3-17 minutes), it was possible that the twice daily dosing employed by Azevedo et al. was insufficient to produce a sustained and meaningful relief of tinnitus (16). Reviewing the literature, I found that most studies that employed oxytocin nasal spray used once or twice daily dosing at low doses, because that was what had been utilized in past studies

without producing serious adverse events. Nearly every study concluded that studies employing higher doses should be attempted in the future.

MacDonald et al. reviewed the safety and side effects of intranasal oxytocin in human studies (17). They reviewed 38 randomized controlled trials conducted over a 20 year period, involving 1529 subjects. These studies used doses from 18-40 IU in doses ranging from once daily to 4 times daily. Most of the participants in the studies (76%) were healthy adults 20-30 years old. Of the 1529 study participants, 926 received oxytocin. Importantly, of the 1529 participants, mild side effects were reported by 18%. The main categories of side-effects included: feeling more calm, relaxed or comfortable, or having more energy (5%), drowsiness, lightheadedness or headaches (6%), and nasal irritation, dryness of the mouth or throat (3%). Importantly, there was a nearly 1:1 relationship between the frequency of side-effects reported in the active and placebo arms. A Wilcoxon signed rank test found no significant difference between the frequency of side-effects reported for oxytocin or placebo.

Although the majority of the studies employed low dose or single doses of oxytocin nasal spray, 2 studies employed 40 IU QID for one week, and 1 study used 40 IU BID over 13 weeks. That long term, doubleblind, placebo-controlled trial studied the effects of high-dose oxytocin nasal spray in 59 women with chronic constipation (18). Twenty-nine women received oxytocin; the authors reported no changes in blood pressure or electrolyte concentrations in either study arm. Five woman reported menstrual irregularities (1 with oxytocin, 4 receiving placebo). Eleven in the oxytocin group and 12 subjects in the placebo group reported mild side-effects consisting of headache, nausea, abdominal pain, weight gain and nasal irritation. The authors found no significant differences between treatment with oxytocin or placebo, and concluded, "the short half-time of oxytocin, in combination with only two administrations daily, might explain the absence of effects on constipation in our study."

Many of the studies of intranasal oxytocin as treatment for a variety of psychiatric disorders in humans were underpowered (19). Clinical trials of oxytocin nasal spray have employed dosages ranging from 15 IU to more than 7000 IU (20). Den Boer and Westenberg, in a double-blinded, placebo-controlled study of 12 patients with obsessive-compulsive disorder (OCD), employed 40 IU oxytocin QID for 6 weeks. There were no changes in blood pressure or weights; in the placebo group, one patient complained of headache and in the oxytocin group, four patients had mild dizziness, and two patients reported dry mouth and mild headache. Additionally, they reported in this paper that they gave 2 patients a threefold higher dose, without producing side-effects. High doses of intranasal oxytocin were assessed in 7 patients with OCD; 5 received 160 IU daily and 2 with 320 IU daily. The authors reported there were no significant changes in blood pressure, pulse, or serum osmolality and "side effects were minimal" but not detailed (21). Although this study employed much higher doses than were previously studied in OCD, the treatment phase only lasted one week and failed to show any significant differences between the active and placebo arms. Here too the authors noted that the failure to obtain therapeutic efficacy may have been due to the short period of drug administration and that "even at high doses, a week of intranasal oxytocin administration does not sufficiently effect the CNS to result in a change in behavior."

2.2 Name and Description of the Investigational Agent

The investigational product is an oxytocin nasal spray composed of: oxytocin/MG/mannitol trituration, magnesium chloride crystals, citric acid anhydrous gran., sodium citrate powder, sterile water for irrigation, and Pcca Mucolox liquid base.

The placebo nasal spray consists of magnesium chloride crystals, citric acid anhydrous gran., sodium citrate powder, sterile water for irrigation, and Pcca Mucolox liquid base. Both placebo and active drug will be handled and stored the same way, in amber glass bottles and kept between 36°F to 46°F (2°C - 8°C).

We believe this study meets the criteria for IND Exemption for the following reasons:

Oxytocin has been tested and is approved by the FDA in different indications. This will be a proof of concept study only, and therefore it is not intended to be reported to the FDA in support of a new indication. If this pilot study, proof of concept study, is successful, we plan to initiate a large-scale study that would then be used to support a new indication, requiring IND application.

We do not intend to use the results of this study to support any change in the advertising of this product and are not affiliated with any sponsors that carry vested interest in the commercial presentations of oxytocin.

2.2.1.1 Clinical Data to Date

See background data in Section 2.1.

2.2.1.2 Dose Rationale (if applicable)

Although the route of administration (nasal spray) used in this study differs from the currently parenteral administration, nasal spray applications of oxytocin have been previously employed for a number of different medical and psychiatric conditions as well as in healthy controls for more than a decade. A recent meta-analysis detailed these studies in which doses of oxytocin ranged from 15 to more than 7000 IU were given without significant adverse events (20). Additionally, recommendations for the standardization of oxytocin nasal administration and guidelines for its reporting were published in the past decade (25). The authors stated "Transmucosal nasal delivery provides a non-invasive alternative route for drugs with poor systemic bioavailability after oral administration. Intranasal administration causes minimal discomfort for the patient, is simple to use, and typically results in high compliance."

Although this study will use a dosage of oxytocin that is higher than used in a previous study of tinnitus (45 IU QID vs 8 IU BID), it is well within the dose range reported in other studies in the psychiatric literature. In those studies, adverse events were rare, non-life threatening and fully reversible.

Additionally, oxytocin nasal spray has been reported in other studies to be very safe (17).

We therefore believe that neither the route of administration nor dose employed in this study would significantly increase the risks (or decrease the acceptability of the risks) associated with the use of the drug product.

2.3 Rationale

The hypothesis is that high dose intranasal oxytocin can significantly reduce tinnitus severity and disability. We hypothesize that treatment with high dose oxytocin nasal spray will result in a significant improvement of tinnitus loudness as measured by VAS when compared to placebo.

Relatively high rates of placebo response have been seen in several studies of tinnitus. As in other subjective symptoms, such as pain and affect, short term improvement after placebo can be meaningful. Therefore, the need of run in phase to determine the true response rate to the active intervention.

2.4 Potential Risks & Benefits

2.4.1.1 Known Potential Risks

Greater than minimal risk. Due to the risk of uterine contractions associated with oxytocin use, female subjects of childbearing potential will be instructed to use a double barrier of birth control and the PI will discuss with them the potential dangers if they were to become pregnant while using the drug. It is possible that high dose oxytocin may cause recruitment of vasopressin leading to a decrease in plasma and an increase in urine osmolality and a decrease in serum sodium levels. As a result, there is the less common risk of developing acute pulmonary edema. The main categories of side-effects include: feeling more calm, relaxed or comfortable, or having more energy (5%), drowsiness, lightheadedness or headaches (6%), and nasal irritation, dryness of the mouth or throat (3%). Patients with any serious adverse events will be immediately withdrawn from the study. However, because of the extremely short half-life of oxytocin, any adverse event would not be expected to be long-lasting.

There is the possibility of bruising from the needle site after blood draws at scheduled visits.

Subjects will be monitored with regular communication to note study challenges or adverse events. Individuals will work with study personnel who have been appropriately trained and access to data will be limited to an as needed basis. Information linking the linkage codes to participant's names, medical record numbers, and social security numbers will be stored in a secure location separate from the medical information and only accessible to members of the study team when needed, after approval by the NYU School of Medicine IRB and Principal Investigator. This access will be documented.

2.4.1.2 Known Potential Benefits

Subjects may or may not directly benefit from being in the study. Close medical monitoring of their symptoms may be a potential benefit if subjects are seen infrequently otherwise. Furthermore, if the medication is effective for tinnitus, participants may indeed improve. However, the overall benefit of participating in this research is that it may help others with tinnitus in the future.

3 Objectives and Purpose

The purpose of this study is to evaluate the effects of high-dose intranasal oxytocin for treating tinnitus.

The primary outcome measurement will be a change in the VAS at 3 timepoints:

1. Comparative endpoint of VAS of all 30 subjects at 9th week of treatment with active drug vs baseline.

2. Comparative endpoint during the cross-over phase of VAS at the 17th visit (15th week of study) between the 15 subjects who received placebo vs the 9th week of the non-blinded phase for the same subjects (when they were on active drug). This endpoint compares the 15 patients that were switched from active to placebo and compares their response on placebo (from the double blind phase) with their response on active drug (from the non-blinded phase) and compares them to the 15 subjects that remained on active drug during the entire study.

3. A parallel group analysis where we compare both arms in the last week of the double-blind phase—so in essence we are comparing those 15 who were on active throughout the entire study to those that started on active and changed over to placebo.

Secondary endpoints of interest are also defined a-priori:

1. A change in the THI by at least one grade contrasting the 9th week (end of the single blinded phase) and the 15th week of the study (end of the double blinded phase) between the 15 subjects who were switched from active drug to placebo.

2. A change in the THI by at least one grade during the last 2 weeks of the double-blind stage (weeks 14 and 15 of the study contrasting those on active drug vs. placebo.

Exploratory endpoints of interest include:

Clinical Global Impression (CGI) measured following the same approach of the primary endpoints. Tinnitus Functional Index (TFI) measured following the same approach of the primary endpoints.

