7.2.3.9 Visit 11: Week 9 (Office Visit)

- Record vital signs and auscultate lungs.
- Review current medications and results of VAS log.
- Collect urine for electrolyte levels and urine osmolality. Perform urine pregnancy test, if applicable.
- Administer THI and CGI-I questionnaires.
- Record adverse events as reported by participant or observed by investigator.
- Study drug reconciliation and record of participant's adherence to treatment program.
- Randomize and dispense new study drug (active drug or placebo nasal spray) to use for the next 2 weeks.

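### The first secondary THI endpoint is a before-after change in the placebo switchers alone, and no planned analysis gives the controlled Week 9 to Week 15 THI contrast

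*Combined protocol and SAP*

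**What the plan says.** Section 3 lists two secondary endpoints on the Tinnitus Handicap Inventory (THI). The first is "A change in the THI by at least one grade contrasting the 9th week (end of the single blinded phase) and the 15th week", taken "between the 15 subjects who were switched from active drug to placebo". No second group is named. The second THI endpoint is controlled: it uses "weeks 14 and 15 of the study contrasting those on active drug vs. placebo".

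The second primary VAS item in the same section also uses Weeks 9 and 15 in the switchers, but adds that it "compares them to the 15 subjects that remained on active drug during the entire study". That item, not the THI endpoint, carries the cross-over label: "Comparative endpoint during the cross-over phase of VAS at the 17th visit".

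Section 4.1 describes the nine weeks before randomisation as non-blinded, with everyone on oxytocin, followed by six double-blind weeks with half on each spray. Sections 4.2.1.2, 9.2, 9.4 and 9.4.3 plan frequencies and percentages of THI change by arm, with week 3 of the blinded phase as the starting point. Section 4.1 calls the secondary metrics exploratory.

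**The concern.** Three things differ between the two THI scores in a switcher. Oxytocin has been withdrawn, six weeks have passed, and a participant who knew the spray was active now knows it may be placebo. A change in grade could come from any of these. The plan recognises the hazard in general terms: Section 2.3 states that "Relatively high rates of placebo response have been seen in several studies of tinnitus", and Section 9.4.2 treats the open-label VAS measure as biased by knowledge of treatment.

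The endpoint also counts a change of at least one grade either way. Losing a useful drug should show as worsening, yet an improvement scores as an event too.

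Section 4.1 says the secondary results will guide a larger study. A switchers-only count, read as the effect of losing oxytocin, could misinform that planning even if no test is done on it.

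**Working it through.** **No figure to reproduce.** The plan gives no expected THI shift rate, and Section 9.5 states n=30 without a rate, standard deviation, power or error level. The check is therefore mainly of design.

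**What each THI analysis compares.**

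| Source | Groups | Times |
|---|---|---|
| Section 3, THI endpoint 1 | Switchers only | Week 9 to Week 15 |
| Section 3, THI endpoint 2 | Active vs placebo | Weeks 14 and 15 |
| Sections 4.2.1.2, 9.2 | By arm | Blinded week 3 to week 6 |
| Sections 9.4, 9.4.3 | By arm | After the blinded week 3 baseline |

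No row has both arms and a Week 9 starting point. The by-arm baseline falls after two weeks on assigned treatment, so any withdrawal effect in those weeks is already in it.

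**What the contrasts estimate.** Write D for the effect of withdrawal, T for time and K for the loss of open-label knowledge, on the scale of mean change.

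- Switchers: D + T + K.
- Continuing-active arm: T + K.
- Difference between arms: D.

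The cancellation assumes that T and K are the same on average in both arms, which randomisation and intact blinding support. Endpoint 1 reports only the first line.

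**Possible size (assumed inputs).** Suppose 20% to 40% shift a grade through T and K alone.

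- Expected events in 15 switchers with no drug effect: 0.20 × 15 = 3 to 0.40 × 15 = 6.
- Expected difference between arms, with the same rate in both: 0.
- Because direction is not specified, 6 events could be six participants worse, or three worse and three better.

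**Are the data there?** Yes. The Visit 11 (Week 9) list has "Administer THI and CGI-I questionnaires", and the Visit 17 (Week 15) list has the same item. Both apply to every participant. By contrast, the detailed lists for the Week 12 and Week 14 phone visits name only the Tinnitus Functional Index.

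**What control costs in precision**, with 15 per arm:

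- Standard error of a mean change, in SD units: within switchers √(1/15) = 0.258; between arms √(2/15) = 0.365.
- 95% half-width for a difference in proportions, 1.96 × √(2p(1−p)/15): p = 0.20 gives 1.96 × √(0.32/15) = 0.29; p = 0.40 gives 1.96 × √(0.48/15) = 0.35.

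**THI threshold.** It varies across the plan: one grade or more (Section 3), more than one grade (4.2.1.2 and 9.2), one point or more (9.4 and 9.4.3), and more than one point (9.4.1).

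**The case against.** The best defence is that Section 9 governs the analysis, summarises THI by arm and never uses the switchers-only contrast. Its week 3 baseline is deliberate: Section 9.4 excludes the first two weeks as a washout. No THI test is planned there. The p < 0.10 criterion in Section 4.1 refers to improvement, not to this contrast. All of that stands and lowers the severity. It does not supply the missing contrast, and Section 3 still presents endpoint 1 as defined in advance.

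Several stronger readings are tempting, but the documents do not support them:

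- *The trial cannot separate withdrawal from time.* It can. There are two randomised sequences, active-active and active-placebo, and the continuing-active arm passes through the same period and the same loss of open-label knowledge.
- *The THI endpoint is presented as part of a cross-over.* That label belongs to VAS item 2, which already names the continuing-active group.
- *The bias must favour oxytocin.* Section 2.3 reports placebo response but says nothing about its fading. A response that persisted after the switch would hide a withdrawal effect.
- *The plan misdescribes its blinding throughout.* The phrase single blinded appears once, and Section 3 itself says non-blinded in VAS item 2.

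**Conclusion.** The point holds for this endpoint. As written in Section 3, THI endpoint 1 is uncontrolled and has no direction, so it cannot distinguish drug withdrawal from time or from loss of open-label knowledge. The plan has no between-arm Week 9 to Week 15 THI analysis to set beside it.

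The size and direction of the bias are unknown. The figure of 3 to 6 events in 15 rests entirely on an assumed 20-40% shift rate and shows only what is possible. The figures also assume exactly 15 per arm with THI at both visits.

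This should be corrected, but it does not threaten the trial: the endpoint is secondary, called exploratory and absent from the Section 9 methods.

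**What to change.** - Redefine THI endpoint 1 in Section 3 as worsening by at least one grade from Visit 11, scored before assignment, to Visit 17. Report it in both arms as a difference in proportions with a confidence interval.
- Report improvement by at least one grade separately. Keep the switchers-only change, labelled descriptive.
- Carry the definition into Section 9.4.3, whose analysis set is now tied to the week 3 baseline, and use one THI threshold throughout Sections 3, 4.2.1.2, 9.2, 9.4, 9.4.1 and 9.4.3.
- In VAS item 2, state that the comparison is the between-arm difference in Week 9 to Week 15 change.
- In Section 3, change single blinded to non-blinded and drop the word cross-over.

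This is wording only: no visit, questionnaire or participant is added. The statistical cost is the loss of precision shown in the working, and with 15 per arm the interval will be wide.
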